981	8.4.1 Clinical Events Committee	
982 983 984	Clinical Primary and Secondary Endpoint events will be adjudicated by the Clinical Events Committee (CEC). The CEC will be made up of the Medical Monitor, Lead Investigator and one independent diabetes expert.	
985 986 987 988	The CEC will adjudicate endpoint events based on review of all available information that is relevant to determining whether protocol-defined clinical endpoint events have occurred during the study as outlined in the CEC Charter. Operational details will be defined in a separate Clinical Events Committee SOP document.	
989	8.4.2 Primary Efficacy Endpoint	
990 991	Percentage of successfully-inserted SteadiSet infusion sets (i.e., not removed within 8 hours of insertion) that are not withdrawn from use prior to 7 days (168 hours) due to either (1), (2), or (3):	
992 993	 Blood Glucose value ≥250 mg/dL with ketones >1.0 mmol/L, in the absence of illness or other physiological stress. 	
994 995 996 997	2. Blood Glucose value ≥250 mg/dL for at least 60 minutes duration, 3 hours or more following a snack or meal event AND failure to respond to up to 2 adequate corrective boluses delivered by the pump with a fall of at least 50 mg/dL. In the absence of BGM testing immediately prior to or following a corrective bolus then CGM values will be used for the primary endpoint analyses.	
998	3. Investigator advises the infusion set should be replaced to assure subject's safety.	

999	8.4.3 Safety Endpoints		
1000 1001 1002	The incidence, severity, and relationship to the investigational device of all reported adverse events (serious and non-serious including DKA and severe hypoglycemia) from day of insertion through day of device removal for each wear period.		
1003		8.4.4 Key Secondary Endpoint	
1004 1005 1006 1007 1008	Proportion (%) of SteadiSet infusion sets withdrawn from use at any time following insertion prior to 7 days (168 hours) as evidenced by one or more of the following device failure modes. NOTE: infusion set removals prior to 168 hours due to miscalculation of date and/or time, along with other removals that cannot be ascribed to the investigational device performance, are excluded from this proportion calculation.		
1009 1010	1.	Infusion set failure as defined in the Primary Endpoint (including any such removals occurring during the first 8 hours following set insertion)	

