1044	3.	Since this is not a randomized trial, the intention-to-treat principle does not apply.	
1045	4.	All reported adverse events will be included in the safety analyses.	
1046		8.6 Analysis of the Primary Efficacy Endpoint(s)	
1047	Analysis will be done separately for each insulin type (Humalog and Novolog).		
1048 1049 1050	Kaplan-Meier estimates will be reported along with a curve used to estimate the proportion of infusion sets that last at least 7 days. Any infusion sets that are removed prior to day 7 without meeting the stated failure criteria will be treated as a censored observation.		
1051 1052 1053	A two-sided 95% confidence interval (95% CI) for the 7-day survival rate will be calculated with a bootstrap to account for the correlated data from having each subject wear multiple infusion sets. A corresponding p-value will be given for the null hypothesis that the true survival probability is 75%.		
1054		8.7 Analysis of the Secondary and Exploratory Endpoints	
1055 1056 1057 1058 1059	pooled Steadis device	ts from the primary analysis are comparable for Humalog and Novolog, then the data will be for secondary analyses. Otherwise, separate analyses will be done by insulin type. Percentage of Set infusion sets not withdrawn from use prior to 7 days (168 hours) as evidenced by the absence of failure, and as defined above, will be analyzed using the same statistical methods as described for the primary efficacy endpoint.	
1060 1061 1062 1063 1064	A paired t-test will be used to compare the central lab HbA1c values measured at the final study visit versus the Day 0 value. A two-sided 95% CI will be given for the mean difference. Only subjects with a central lab value at both times will be included in this analysis. Similar pre- post comparisons will be done with selected CGM metrics. These will include data from the final 14 days of the study compared with the baseline CGM data.		
1065	Survey	and pain assessment results will be tabulated.	
1066 1067		ner continuous and binary outcomes will be summarized as appropriate to their distributions (i.e., SD), median (IQR), or n (%)). Plots and 95% CI will be calculated for selected outcomes.	
1068 1069		metrics will be calculated over the entire study period (24-hour, daytime, and nighttime) and by week (24 hour only).	
1070	Hyperg	glycemia Trend in Days 1-3 versus after Day 3	

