- will use Humalog[™] (insulin Lispro) and ~120 who will use NovoLog[™] (insulin aspart).
- Assuming N=120 participants completing the study for each insulin type, a null hypothesis
- stating that the success rate is 75%, a true success rate of 83%, 12 wear periods per participant,
- 28 within-participant correlation of at most 0.4, and two-sided type 1 error rate of 5% we will have
- statistical power of 87% for the evaluation of each of the two insulin types. Note that with only 9
- wear periods per participant we would still have 86% power.

5 Outcome Measures

- 32 The Primary and Key Secondary Efficacy endpoints will be analyzed by infusion set. If more
- than one type of insulin is used during an infusion set wear period, that wear will be excluded
- 34 from analyses of the Primary and Key Secondary Efficacy endpoints. When the other Secondary
- outcomes or the Exploratory outcome are analyzed separately by insulin type, any wear period

- during which more than one type of insulin is used will be excluded from the analysis, except
- where specified.

38 5.1 Clinical Events Committee

- 39 Clinical Primary Efficacy and Key Secondary events will be adjudicated by the Clinical Events
- 40 Committee (CEC). The CEC's composition and role are described in the Clinical Events
- 41 Committee SOP and Charter.

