- wears of the investigational infusion set will be included; all data from a personal pump (if used
- during the study) will not be counted. Any dropouts will be counted as zero use for the remainder
- of the study.

168 **5.8.1 Overall**

- Overall insulin metrics will be calculated over the entire follow-up period. A minimum of 21
- 170 complete days are required to calculate total daily insulin metrics. Baseline insulin delivery will
- be obtained from the Demographics CRF, which describes the week prior to the Screening visit.

172 5.8.2 Insulin Metrics by Study Week

- 173 Insulin metrics will be calculated for each week of the study. A minimum of 6 complete days of
- insulin data is required to calculate insulin metrics for a week.

175 5.8.3 Insulin Metrics by Day of Infusion Set Wear

- 176 Insulin metrics will also be tabulated by day of infusion set wear over the entire study. A day is
- each subsequent 24-hour period since the current set is inserted. Participants must provide a
- minimum of six complete days of insulin data to be included in the calculation for insulin metrics
- on that day.

180 **6 Description of Statistical Methods**

181 **6.1 Analysis Cohorts**

- Analysis of the Primary Efficacy endpoint will include participants who successfully insert at
- least one investigational infusion set.
- 184 The analysis of the Key Secondary endpoint and the safety endpoints will include all participants
- who attempt to insert at least one investigational infusion set.
- Analyses of all other endpoints will include participants who successfully insert at least one
- investigational infusion set. Intention-to-treat is not relevant since this is not a randomized trial.

188 **6.2** Analysis of the Primary Endpoint

- The proportions of successfully inserted investigational infusion sets that last at least 7 days will
- be tabulated overall and by infusion set location. Reasons reported for removal (main and
- secondary) will be tabulated. All tabulations will be done separately for each insulin type
- 192 (Humalog and Novolog).
- Analysis will be done separately for each insulin type. Kaplan-Meier estimates will be reported
- along with a curve used to estimate the proportion of infusion sets that last at least 7 days.
- 195 Successfully inserted infusion sets that are removed prior to day 7 without meeting the stated
- 196 failure criteria in section 5.2 (Primary Efficacy Endpoint) will be treated as censored

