- 285 whether it corresponded to an infusion set failure. The circumstances of all reportable adverse
- events will be summarized.

287

8 Intervention Adherence and Retention Analyses

- The following tabulations and analyses will be performed overall and by insulin type to assess
- intervention adherence, protocol adherence, and retention:

- Flowchart of study participants
- Number of investigational infusion sets worn
- Gaps of ≥3 hours in infusion set wears
- Tabulation of infusion set removal cases reviewed by the CEC and their determinations
- Distribution of infusion set wear per participant
- Visit completion rates for each follow-up visit
- Protocol deviations
- Numbers of and reasons for unscheduled visits and phone calls
- Participant adherence to expected BG/ketone/correction bolus procedures prior to set removals before 7 days

9 Baseline Descriptive Statistics

- 301 Baseline demographic and clinical characteristics of the cohort of all enrolled participants with at
- least one wear will be summarized in a table. For continuous variables, appropriate summary
- statistics will be given. For discrete variables, number and percentage will be reported for each
- 304 category.

300

- The following baseline characteristics will be included in the table:
- 306 Age
- 307 Sex
- 308 Race/ethnicity
- Diabetes duration
- Education
- Household Income
- Health Insurance
- 313 ◆ HbA1c
- 314 BMI

322

- CGM metrics
- \circ % Time >180 mg/dL
- \circ % Time < 70 mg/dL
- o Estimated HbA1c
- Insulin type—Humalog or Novolog
- Infusion set type in use at time of study screening

10 Planned Interim Analyses

No formal interim efficacy analyses are planned for this study.

324 11 Subgroup Analyses

- 325 The Primary Efficacy and Key Secondary outcomes as well as CGM hyperglycemia metrics (%
- 326 time > 180 mg/dL, % time > 250 mg/dL, mean glucose), HbA1c, and insulin metrics will be
- 327 explored according to the factors below.
- Hours 0–<72 versus hours 72–168 since infusion set insertion
- Infusion set location
- Whether any additional taping and/or skin adhesive barrier wipe was used to secure the infusion set on the day that it was inserted
- Units per day of insulin (<25 versus ≥25)
- Diabetes duration

334

335

336

337

351

352

353

354

355

356

357

358

359

360

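### Only one of three Clinical Events Committee members is described as independent, and no planned analysis re-estimates the 7-day rate without the committee's adjudication

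*Protocol*

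**What the plan says.** - **Composition.** Protocol 8.4.1: "The CEC will be made up of the Medical Monitor, Lead Investigator and one independent diabetes expert". It gives the committee the primary and secondary endpoint events to adjudicate.
- **Decision rule.** Neither document gives a voting, quorum or recusal rule. Protocol 8.4.1 refers to a CEC Charter and adds that "Operational details will be defined in a separate Clinical Events Committee SOP" document. SAP 5.1 says only that the committee's "composition and role are described in the Clinical Events" Committee SOP and Charter.
- **Consequence of not meeting the criteria.** Protocol 8.6: "Any infusion sets that are removed prior to day 7 without meeting the stated failure criteria will be treated as a censored observation". SAP 6.2 and 6.3.1 do the same for the primary and key secondary endpoints.
- **Planned reporting.** SAP 8 lists "Tabulation of infusion set removal cases reviewed by the CEC and their determinations", overall and by insulin type. SAP 6.2 tabulates the main and secondary reasons reported for removal, and the proportion of successfully inserted sets lasting at least 7 days.
- **Sensitivity analyses.** Protocol 8.5 has the term in its heading but lists none. SAP 6.2 adds none.

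**The concern.** The primary result is a Kaplan-Meier 7-day survival rate tested against 75%, separately for each insulin type. A removal judged to meet a criterion is an event. One judged not to meet it is censored, and censoring raises the estimate relative to counting an event. There is no control arm in which a tendency in adjudication, in either direction, would cancel. The study is open-label, and only one member of the committee is described as independent.

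The committee can plausibly reach a different answer from the site, for two reasons.

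- **Different definitions.** Protocol 1.4 tells sites when failure is established. Protocol 8.4.2 and SAP 5.2 define the endpoint, and the two do not coincide (see the comparison in the working).
- **Judgement.** The endpoint text needs rulings on whether there was illness or other physiological stress, whether boluses were adequate, and whether CGM values should stand in for missing meter values.

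A reader of the final report would see what the committee decided. That reader would not see how much of any margin over 75% depends on those decisions.

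**Working it through.** **1. Section 1.4 beside Section 8.4.2.** Under Protocol 1.4, take a set where fingerstick glucose falls by at least 50 mg/dL after the second correction bolus but does not drop below 250 mg/dL within six hours. Failure is then established. Under 8.4.2, criterion 2 requires the absence of a 50 mg/dL fall, so this set does not meet it. It does not meet criterion 1 either if ketones stay at or below 1.0 mmol/L. It counts as a failure only if criterion 3 (investigator's advice to replace) is held to apply. A failure established at the site therefore need not be an endpoint failure under criteria 1 or 2.

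**2. Inputs for the arithmetic (Protocol 8.3, SAP 4).** 120 participants per insulin type, 12 wears each, null 75%, alternative 83%, within-participant correlation 0.4, two-sided 5%.

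- Design effect = 1 + (12 − 1) × 0.4 = 5.4
- Effective n = 120 × 12 / 5.4 = 1440 / 5.4 = 266.7

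**3. The plan's own figure.** Null standard error = √(0.75 × 0.25 / 266.7) = 0.0265. The estimate needed to reject is 0.75 + 1.96 × 0.0265 = 0.802. Standard error at 83% = √(0.83 × 0.17 / 266.7) = 0.0230. Power = Φ((0.83 − 0.802) / 0.0230) = 88.8%, or 87.2% with a continuity correction. An exact binomial calculation gives 87.6%. The stated 87% is reproduced, so the inputs are a fair basis for what follows.

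**4. Effect of reclassification.** The documents give no rate, so the share f of failures moved to censored is an assumption. If f is the same at all wear times and reclassification is random, the failure hazard is multiplied by (1 − f), and the Kaplan-Meier 7-day rate moves from S to S^(1 − f). At S = 0.75 there are 0.25 × 1440 = 360 failures per insulin type.

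| f | Sets moved | 7-day estimate | Chance of a result above 75% by the test |
|---|---|---|---|
| 0 | 0 | 75.0% | 2.5% |
| 5% | 18 | 0.75^0.95 = 76.1% | 5.8% |
| 10% | 36 | 0.75^0.90 = 77.2% | 12.1% |
| 20% | 72 | 0.75^0.80 = 79.4% | 38.0% |

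The last column is 1 − Φ((0.802 − S′) / √(S′(1 − S′) / 266.7)), where S′ is the shifted estimate. It ignores the small loss of information from the extra censoring.

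**5. Share that would reach the boundary.** f = 1 − ln(0.802) / ln(S). At a true 75% this is about 23% of failures (84 sets). At a true 77% it is about 16% (52 sets).

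**6. At the planned 83%.** The same shares move the estimate to 83.8%, 84.6% or 86.2%. Rejection is already likely there, so the effect is mainly on the reported rate.

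**7. Own-site cases.** The documents do not say whether the Lead Investigator enrols. If so, the cap of 25 completers per site (Protocol 2.1) allows 25 / 240 = 10.4% of completers overall, or 25 / 120 = 20.8% of one insulin cohort if all 25 used the same insulin.

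**The case against.** The strongest objection is that the decisive rules are in documents not available here. A reader might infer from the composition that two study-affiliated members can outvote the independent expert and turn failures into censored sets. The documents do not support that. They state no majority rule, and the Charter may require unanimity, a quorum or own-site recusal. They also do not say who employs the Medical Monitor. This stands in full.

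A reader might also infer that nothing in the plan shows what adjudication did. That is not so. SAP 8 tabulates the committee's determinations and adherence to the glucose, ketone and correction-bolus steps before early removals. SAP 6.2 tabulates reported reasons. Its proportion of sets lasting at least 7 days, read literally, does not depend on adjudication and is a crude lower bound. But that proportion also counts accidental and other removals unrelated to failure as not lasting, so it cannot isolate the effect. None of these tables gives a Kaplan-Meier rate, clustered interval or p-value on the site's classification.

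The committee's room for judgement is limited. Criteria 1 and 2 rest on numerical thresholds, supported by device uploads and a structured interview. The Protocol Summary also points from the endpoint to Section 1.4 for further detail, so the committee might apply the six-hour rule. Sections 1.3.1 and 8.4.2 and SAP 5.2 contain no such pointer, so this remains open.

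Finally, adjudication can also move sets into failure, and the sites are themselves unblinded. The site's classification is a second view, not a truth standard. That stands, and it is why changes should be counted in both directions.

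**Conclusion.** The concern holds in a limited form. One of three members is described as independent, the decision rule is outside the documents, and no planned analysis shows whether a conclusion against 75% depends on adjudication. The difference between Protocol 1.4 and 8.4.2 makes some disagreement between site and committee plausible.

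The size is illustrative. It assumes correlation 0.4, random one-way reclassification at a constant rate, and 12 wears from each of 120 participants. At a true 75%, even 20% of failures moved leaves the expected estimate at 79.4%, just under the roughly 80% needed, although the chance of a false favourable result rises well above 2.5%.

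It would go too far to say that adjudication will bias the result upward or that failures will be downgraded: no reclassification rate or direction is documented. This is a worthwhile, low-cost addition to the analysis, not evidence of a defective committee.

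**What to change.** 1. **SAP 6.2 and 6.3.1.** Add a sensitivity Kaplan-Meier estimate of the 7-day rate using the site's classification before adjudication. Use the same participant-level bootstrap interval and p-value, by insulin type. Name the CRF item that supplies the classification; Protocol 6.3 already puts infusion set failures on a protocol-specific form.
2. **Alongside the SAP 8 tabulation.** Report the number of sets the committee changed from failure to non-failure, and from non-failure to failure.
3. **Protocol 1.4 and 8.4.2 (with SAP 5.2).** Reconcile the passages so that it is clear whether a set established as failed under 1.4 is an endpoint failure. Otherwise the sensitivity analysis will mix a difference in definition with a difference in judgement.
4. **CEC Charter.** Confirm that it covers recusal of the Lead Investigator for sets from his or her own site, if the Lead Investigator enrols.

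I would not give the independent expert a veto over changes in one direction only. That would tilt the result the other way and is a debatable design choice.

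The cost is some SAP wording, one rerun of an existing program and a check of the Charter. No new members or data should be needed, provided the site's classification is kept as entered. The downside is a second, possibly lower, success rate in the report.

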1011 1012	2.	Evidence of infusion set site infection defined as requiring treatment or at the investigator's judgment	
1013 1014	3.	Cannula dislodgement from subcutaneous (SC) space (with or without liquid leakage at the cannula insertion site)	
1015 1016		 Leakage at the cannula insertion site may or may not be deemed by the investigator to constitute infusion set failure following consultation with the study subject 	
1017 1018		b. Accidental removal events (e.g., tubing caught on doorknob) are excluded from this proportion calculation	
1019	4.	Occurrence of a non-resolvable pump occlusion alarm,	
1020 1021	5.	Other device malfunction (e.g., inability to pierce skin, bending, or other malformation that might impact insulin infusion, securement failure)	
1022	6.	Presence of pain of sufficient severity to prompt early removal of infusion set	
1023 1024	7.	Any other event that can be ascribed to the investigational device performance that results in failure of insulin delivery	
1025		8.4.5 Other Secondary Endpoints	
1026 1027	1.	Standard glucose control measures obtained from CGM, including observed hyper- and hypoglycemic episodes, time in range, mean 24-hour glucose, and other measures	
1028 1029	2.	Total daily insulin dose, basal dose, bolus dose, and bolus basal ratio, overall, and by day of infusion set wear.	
1030 1031	3.	Subject tolerability levels for the infusion set insertion as assessed by a pain scale of 0 to 100 with zero being no pain and 100 being significant pain	
1032	4.	Hyperglycemia trends in days 1-3 versus after day 3	
1033 1034 1035	5.	Infusion set performance (including set failures as defined above and also glucose metrics, insulin doses, pump occlusion alarms and hyperglycemia trends) in subjects who use low doses (e.g., <25 units/day) of insulin and in subjects who experience frequent stops and start of pump use	
1036		8.4.6 Exploratory Endpoint	
1037	1	Hh A 1c change from baseline to the end of study participation	

1038		8.5 Analysis Datasets and Sensitivity Analyses	
1039 1040	1.	Only wears of the investigational infusion set will be included in the analysis (i.e., any wear of a personal infusion set will be excluded)	
1041 1042 1043	2.	All subjects with at least one wear of the investigational infusion set and all such wears will be included in the primary and secondary efficacy analyses. Subjects who complete at least six wear periods will be considered as "completers."	

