
1338 Simic et al. performed a clamp study with 16 subjects assessing a new extended-wear infusion set with an anti-inflammatory coating and Lantern technology (ConvaTec) and found that while insulin absorption 1339 decreased over wear time, it was also significantly faster 4 and 7 days after insertion. None of the patients 1340 experienced severe hypoglycemia over a period of 7 days. The authors claim that increased rate of 1341 absorption my facilitate better postprandial control.²³ 1342 1343 A.3 Experience with Extended Wear (>3 days) Patel et al. performed a randomized crossover clinical trial to compare the performance of Teflon versus 1344 stainless steel insulin infusion sets in ambulatory humans for up to 1 week. The subjects used a Quick-Set 1345 1346 or a Sure-T CSII cannula until the infusion set failed or was worn for 1 week. After 7 days, both types of infusion sets had a 64% failure rate. Eighty-seven percent of the steel sets and 77% of the Teflon sets 1347 were functioning after 3 days (this number includes the 15% that failed on the first day because of 1348 1349 kinking), after 5 days 68% of the steel and 59% of the Teflon sets were functioning, after 6 days 53% of the steel and 46% of the Teflon sets were functioning, and at the end of 7 days 32% of the steel and 32% 1350 1351 of the Teflon sets were functioning. Overall, 30% failed because of hyperglycemia and a failed correction dose, 13% were removed for pain, 10% were pulled out by accident, 10% had erythema and/or induration 1352 of >10 mm, 5% fell out because of loss of adhesion, and 4% were removed for infection. The main 1353 1354 predictor of length of wear was the individual subject. There was no increase in hyperglycemia or daily 1355 insulin requirements when an infusion set was successfully used for 7 days.²⁴ Waldenmaier et al. tested extended wear (≥7 days) of commercial steel and Teflon insulin infusion sets in 1356 40 adult subjects on insulin pump therapy. 66% of 160 inserted infusion sets were used for 7 days with no 1357 1358 obvious difference between steel and Teflon infusion sets (mean wear time was 6.2 days). The main reasons for early infusion set replacements were occlusions (19%), adhesive issues (4%), and accidental 1359 removal (4%). Comparing glycemic control during day 1-3 and 1-7, there was no difference in mean BG 1360 and insulin dose. The authors concluded that infusion set replacement intervals may be individualized 1361 beyond the currently labeled maximum use duration.8 1362 Lal et al. assessed longevity of the previously mentioned ConvaTec infusion set in a pilot study including 1363 22 subjects. 45% of the novel infusion sets lasted 10 days, with a median wear time of 9.1 days. While the 1364 mean BG concentration increased significantly over time, the total daily insulin dose did not change 1365 throughout 10 days of set wear.⁹ 1366 Recently, Medtronic reported an overall wear period success rate of 74.8% at 7 days using an extended 1367 wear infusion set (Buckingham et al., poster, American Diabetes Association annual meeting, 2021), 1368 leading to device approval by the FDA (510k). There has been no marketing experience reported for 1369 this device. 1370 1371 Summarizing these various studies of cannula wear time, it appears that currently marketed infusion sets 1372 have limited life span, and room for improvement is present.

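### Does the key secondary endpoint need a written rule and a sensitivity analysis to separate accidental removals from securement failures?

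*Protocol*

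**What the plan says.** The key secondary endpoint (Protocol 8.4.4, repeated in SAP 5.3) is the proportion of sets withdrawn before 168 hours through any of seven device failure modes. Mode 3 is dislodgement of the cannula, with a carve-out at 3b: "Accidental removal events (e.g., tubing caught on doorknob) are excluded from this proportion calculation". Mode 5 reads "Other device malfunction (e.g., inability to pierce skin, bending, or other malformation that might impact insulin infusion, securement failure". A note above the list removes date and time errors, "along with other removals that cannot be ascribed to the investigational device performance, are excluded from this proportion calculation".

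Protocol 8.7 and SAP 6.3.1 analyse the endpoint by the primary's method: Kaplan-Meier with a bootstrap confidence interval. Early removals that do not meet the failure criteria are censored (Protocol 8.6, SAP 6.3.1).

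On classification, Protocol 8.4.1 states: "Clinical Primary and Secondary Endpoint events will be adjudicated by the Clinical Events Committee". It leaves operational details to a Charter and an SOP that are not among the documents available here. SAP 8 lists this output: "Tabulation of infusion set removal cases reviewed by the CEC and their determinations". SAP 6.2 tabulates, by insulin type, the main and secondary removal reasons and the proportion of successfully inserted sets lasting at least 7 days. Protocol 8.5 is headed "Analysis Datasets and Sensitivity Analyses" but lists no sensitivity analysis, and the SAP has none for this endpoint.

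**The concern.** When a set comes off early, the label it receives decides whether it is an event or a censored observation. Dislodgement and securement failure count; accidental removal does not. Beyond whether the device can be blamed and the doorknob example, neither document says what evidence separates them. Neither says that removals reported as accidental are always sent to the committee.

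The trial is open-label and single-arm, so no control group would carry the same labelling error. This is also the only efficacy endpoint that covers all device failure modes. The protocol's own literature shows that both kinds of removal occur. In one study in Appendix A.3, "10% were pulled out by accident" and "5% fell out because of loss of adhesion"; in another, accidental removal and adhesive problems took 4% each. If many true securement failures were labelled accidental, the reported success rate would be too high, and no planned interval would show by how much.

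**Working it through.** **Inputs.** Protocol 8.3: 120 subjects per insulin type, 12 wears each, within-subject correlation 0.4, null 75%, true success 83%, two-sided alpha 0.05. Protocol Appendix A.3: observed accidental-removal shares a = 4% and 10%. Assumptions: those shares, from other sets, apply to SteadiSet; hazards are constant over 168 hours; and 83%, the primary's planning rate, stands in for this endpoint, for which none is given.

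**1. The plan's own figure.** The design effect is 1 + 11 × 0.4 = 5.4, so the effective n is 1440 / 5.4 = 266.7. Power is 88.9% by the normal approximation and 87.6% by the exact binomial, against 87% stated. With 9 wears the effective n is 1080 / 4.2 = 257.1 and power is 87.6% and 87.0%, against 86% stated. Both reproduce, so the same effective n is used below.

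**2. Precision.** Half-width at 83%: 1.96 × √(0.83 × 0.17 / 266.7) = 4.5 points.

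**3. All accidental removals recounted as failures.**
- Simple product S × a: 0.83 × 0.04 = 3.3 points; 0.83 × 0.10 = 8.3 points. With S = 75%: 3.0 and 7.5 points.
- Constant hazards: λf = −ln 0.83 = 0.186. Solve λa/(λa + λf) × (1 − exp(−(λa + λf))) = a, which gives λa = 0.045 (4%) and 0.116 (10%). Success becomes exp(−(λa + λf)) = 79.4% or 73.9%, a fall of 3.6 or 9.1 points. With S = 75% the fall is 3.4 or 8.6 points.

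The outer bound is therefore about 3 to 9 points.

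**4. Half recounted.** 0.83 × exp(−λa/2) = 81.2% or 78.3%, a fall of 1.8 or 4.7 points.

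**5. What SAP 6.2 already shows.** Under the same model the share of sets still in place at 168 hours is exp(−(λa + λf)), which is the all-recounted figure in step 3. Every early removal, whatever its label, lowers that tabulated proportion. For successfully inserted sets it is therefore a floor on success under any reclassification. It lacks an interval and omits sets removed within 8 hours.

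**6. Excluded versus censored.** The definition speaks of exclusion; the analysis sections censor. Dropping these sets from the denominator would give 82.7% (a = 4%) or 82.1% (a = 10%) against 83% by Kaplan-Meier, a difference of 0.3 or 0.9 points. At S = 75% the differences are 0.5 and 1.2 points. Protocol 8.6 and 8.7 settle the matter in favour of censoring.

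**7. Does a conclusion turn on it?** The endpoint adds six failure modes to the primary's, so 83% is a favourable starting point. Adding only the 4-5% adhesion loss from Appendix A.3 gives 0.83 × 0.96 = 79.7% or 0.83 × 0.95 = 78.9%. Against 75%, with effective n 266.7, p is then about 0.06 or 0.12 before any accidental removal is relabelled. A change from clear significance to none cannot be attributed to the labelling.

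**The case for a change.** The strongest case for acting is that a removal reported as accidental may never reach the committee, since it adjudicates endpoint events and such a removal is by definition not one. Even perfect adjudication would not test whether censoring is unrelated to impending failure. The 75% null arguably carries over too, because the synopsis describes Kaplan-Meier for both endpoints and then the 75% p-value. One more run of planned code would cost little.

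Part of this stands. Routing to the committee is not spelled out, and no interval is planned under another classification. Three things limit its weight.

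- The committee's task is to decide whether events meeting the definition occurred, using all relevant information (Protocol 8.4.1), and its rules sit in documents that cannot be seen here. A missing rule cannot be inferred from that. Classification also need not rest on the participant's account alone: participants must contact the site before removing a set early and must return all used parts (Protocol 3.1.2), and a questionnaire accompanies each removal (Protocol 3.4).
- Protocol 8.2 ties the 75% hypothesis to the primary endpoint. No power or success criterion is given for the key secondary, so a p-value there would be descriptive.
- Labelling errors can also run the other way, with true accidents counted as securement failures, which would understate success.

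SAP 6.3.1's censoring sentence mentions only successfully inserted sets, whereas this endpoint starts at insertion. Protocol 8.6, applied through 8.7, covers any set removed early, so analysts have a rule for the rest.

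**Conclusion.** No change is needed. This is operational detail left to the committee's own documents, not a flaw in the endpoint or its analysis. The censoring rule is explicit, and the estimate is sound if classification is right and these removals are unrelated to impending failure. The planned tables of removal reasons, committee determinations and crude 7-day proportions let a reader see how much could depend on labelling.

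The possible movement is about 3 to 9 points if every accidental removal were really a device failure, and about 2 to 5 points if half were. Both ranges assume that the 4-10% shares reported for other sets apply to SteadiSet, that hazards are constant, and that success is near 83%. The upper part exceeds the 4.5-point half-width, but it needs both the higher cited rate and extensive mislabelling in one direction. The mismatch between exclusion and censoring is a matter of wording worth about 1 point at most.
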